3.2 Inclusion Criteria

A subject will be considered eligible for inclusion in this study only if all of the following criteria are met:

1. Subjects must provide written informed consent prior to performance of study specific procedures or assessments, and must be willing to comply with treatment and follow up.
 - a. Procedures conducted as a part of routine clinical management of the subject (e.g., blood count, imaging study) and obtained prior to signed informed consent may be utilized for Screening or Baseline purposes provided these tests are obtained as specified in the protocol).
2. Subjects must have measurable or evaluable disease. Disease sites that are evaluable for progression but not measurable per RECIST guidelines version 1.1 include:
 - a. Bone lesions
 - b. Previously irradiated lesions
 - c. Cutaneous manifestations (non-discrete lesions only)
3. Age \geq 18 years.
4. Postmenopausal women defined by one of the criteria:
 - a. No spontaneous menses for at least 12 months if the subject is \geq 50 years old;
 - b. Amenorrheic for at least 12 months if the subject is < 50 years old, with serum estradiol within the institutional postmenopausal range;
 - c. Bilateral oophorectomy;
 - d. If prior hysterectomy but intact ovaries, must be \geq 55 years old, or have serum estradiol within the postmenopausal range;
 - e. If premenopausal, must be on a GnRH agonist (leuprolide or goserelin) with serum estradiol levels within the institutional postmenopausal range.
5. Eastern Cooperative Oncology Group (ECOG) performance status (PS) \leq 2.
6. Histologically or cytologically confirmed estrogen receptor (ER) and/or progesterone receptor (PgR) positive carcinoma of the breast with unresectable, locally advanced and/or metastatic (AJCC Stage IV) disease.

7. Subjects must have received prior hormonal therapy for the treatment of breast cancer as follows:
 - a. Progression must be documented while taking a nonsteroidal aromatase inhibitor including anastrozole or letrozole.
 - b. If hormonal therapy was administered in the adjuvant setting, subjects must have received therapy for at least 6 months prior to developing metastatic disease.
 - c. If hormonal therapy was administered in the metastatic setting, subjects must have received therapy for at least 3 months prior to progression
8. Subjects whose tumors overexpress ErbB2 are eligible provided that they have progressed following therapy which included trastuzumab and/or lapatinib.

Note for prior lapatinib: Subjects must have completed therapy with lapatinib at least 7 days prior to the first dose of study drug.

Note for prior trastuzumab: Subjects who received Q3 weekly, Q2 weekly or Q1 weekly must have completed therapy with trastuzumab at least 3 weeks, 2 weeks or 1 week, respectively, prior to the first dose of study drug.

9. Adequate hematologic and hepatic function as defined in Table 1.

Table 1 Definitions for Adequate Hematologic and Hepatic Function

System	Laboratory Values
Hematologic	
Absolute neutrophil count (ANC)	$\geq 1.0 \times 10^9/L$
Hemoglobin ^a	$\geq 9 \text{ g/dL} (5.6 \text{ mmol/L})$
Platelets	$\geq 100 \times 10^9/L$
Prothrombin time (PT) or international normalized ratio (INR) ^b	$\leq 1.2 \times \text{ULN}$
Activated partial thromboplastin time (aPTT)	$\leq 1.2 \times \text{ULN}$
Hepatic	
Total bilirubin	$\leq 1.5 \times \text{ULN}$ (except in patients with Gilbert's)
Alanine amino transferase (ALT) and Aspartate aminotransferase (AST) ^c	$\leq 2.5 \times \text{ULN}$
Renal	
Serum creatinine	$\leq 1.5 \text{ mg/dL} (133 \text{ } \mu\text{mol/L})$
Or, if $>1.5 \text{ mg/dL}$: Calculated creatinine clearance	$\geq 30 \text{ mL/min}$
Quantitative urine protein by dipstick	≤ 100
Urine Protein to Creatinine Ratio (UPC) ^d	≤ 1

- a. Subjects may not have had a transfusion within 7 days of screening assessment.
- b. Subjects receiving anticoagulant therapy are eligible if their INR is stable and within the recommended range for the desired level of anticoagulation.
- c. Concomitant elevations in AST/ALT above $1.0 \times \text{ULN}$ (upper limit of normal) are not permitted. Bilirubin ≤ 1.5 except if Gilbert's (elevation due to direct bilirubin)
- d. A UPC is required only if the urine protein is > 100 . If UPC > 1 , then a 24-hour urine protein must be assessed. Subjects must have a 24-hour urine protein value $< 1 \text{ g}$ to be eligible.

10. Subjects must have discontinued hormone replacement therapy (HRT) (e.g., conjugated estrogens tablets, USP or premarin), at least 28 days prior to receiving the first dose of randomized therapy.
11. Radiotherapy prior to initiation of therapy is allowed to a limited area (e.g., palliative treatment for painful bone metastases), if it is not the sole site of disease. Subjects must have completed treatment at least one week prior to starting study drugs, and must have recovered from all treatment-related toxicities.
12. Bisphosphonate or RANK ligand inhibitor therapy for bone metastases is allowed. Prophylactic use of bisphosphonates in subjects without bone disease, except for the treatment of osteoporosis, is not permitted;
13. Ability to swallow and retain oral medication.

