Endothelial cells exposed to the supernatants of estradiol treated breast cancer cells develop increased levels of VEGFR2 compared to controls. This increase in VEGFR2 supports previous findings that endothelial cells containing estrogen receptors exhibit a proliferative response to estradiol[8-10]. In addition, estrogen has been associated with the inhibition of apoptosis of cultured human endothelial cells, and therefore indicates the creation of a pro-angiogenic environment[10].

Estradiol increases intracellular levels of VEGF mRNA and protein in breast cancer cell lines as well as extracellular levels of VEGF protein [11]. Additionally, estradiol treatment of breast cancer cell lines decreased extracellular sVEGFR1, a soluble form of VEGFR1 that is believed to sequester extracellular VEGF and act as an antiangiogenic factor[11, 12]. This decrease was also observed in an *in vivo* xenograft models of breast cancer in nude mice[12].

These data indicate that estrogen acts directly on breast cancer cells to induce angiogenesis by creating a proangiogenic environment. Furthermore, subjects whose tumors have lower sVEGFR1/VEGF ratios tend to have a poorer prognosis compared to those with higher ratios[13, 14]. VEGF may be an important target for hormone receptor-positive breast cancer[15]. In patients with operable breast cancer, neoadjuvant antiestrogen therapy with tamoxifen reduced breast cancer angiogenesis in responding tumors as measured by microvessel count (MVC)[16].

These data support the hypothesis that estradiol can modulate angiogenesis in breast cancer, and that angiogenesis is one mechanism of resistance to hormone directed therapy. Both estrogen and angiogenesis are essential for the development and progression of breast cancer, making the targeting both pathways in combination appealing.

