3.3 Exclusion Criteria

Subjects meeting any of the following criteria must not be enrolled in the study:

1. Prior use of pazopanib or other agents targeting angiogenesis pathway (such as bevacizumab, sunitinib, or sorafenib) in the metastatic setting
2. Premenopausal levels of estradiol, or ongoing menses (see definitions of menopause above).
3. Known central nervous system (CNS) metastases or leptomeningeal carcinomatosis. Screening with CNS imaging studies (computed tomography [CT] or magnetic resonance imaging [MRI]) is required only if the subject has clinical findings suggestive of CNS metastasis.
4. History of another active malignancy.
Note: Subjects who have had another malignancy and have been disease-free for 5 years, or subjects with a history of completely resected non-melanomatous skin carcinoma or successfully treated *in situ* carcinoma are eligible.
5. Clinically significant gastrointestinal abnormalities which might interfere with oral dosing, including, but not limited to:
 - a. Malabsorption syndrome
 - b. Major resection of the stomach or small bowel that could affect the absorption of study drug
 - c. Inflammatory bowel disease
 - d. Ulcerative colitis, or other gastrointestinal conditions with increased risk of perforation
 - e. History of abdominal fistula, gastrointestinal perforation, or intra-abdominal abscess within 28 days prior to beginning study treatment
6. Presence of uncontrolled infection.

7. Prolongation of corrected QT interval (QTc) >480 msecs.
8. History of any one or more of the following cardiovascular conditions within the past 6 months:
 - a. Angioplasty or stenting
 - b. Myocardial infarction
 - c. Unstable angina
 - d. Coronary artery by-pass graft surgery
 - e. Symptomatic peripheral vascular disease
9. Class II, III or IV congestive heart failure, as defined by the New York Heart Association (NYHA).
10. Use of an investigational agent, including an investigational anti-cancer agent, within 14 days prior to the first dose of study drug.
11. Prior use of an investigational drug that targets VEGF or VEGF receptors.
12. Any ongoing toxicity from prior anti-cancer therapy that is $>$ Grade 1 and/or that is progressing in severity.
13. Poorly controlled hypertension (defined as systolic blood pressure (SBP) of ≥ 140 mmHg or diastolic blood pressure (DBP) of ≥ 90 mmHg).

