Medications that inhibit CYP3A4 may result in increased plasma pazopanib concentrations. Selection of an alternate concomitant medication with no or minimal potential to inhibit CYP3A4 is recommended. A dose reduction to 400 mg pazopanib should be considered when it must be co-administered with strong CYP3A4 inhibitors.

Strong CYP3A4 inhibitors include (but are not limited to):

- Antibiotics: clarithromycin, telithromycin, troleandomycin
- HIV: protease inhibitors (ritonavir, indinavir, saquinavir, nelfinavir, amprenavir, lopinavir)

- Antifungals: itraconzaole, ketoconazole, voriconazole, fluconazole
- Antidepressants: nefazodone
- Diet: grapefruit, seville oranges, starfruit, and their juices

CYP3A4 inducers may decrease plasma pazopanib concentrations. Selection of an alternate concomitant medication with no or minimal enzyme induction potential is recommended.

Drugs that induce CYP3A4 and may decrease pazopanib plasma concentrations include (but are not limited to):

- Glucocorticoids: cortisone (>50 mg), hydrocortisone (>40 mg), prednisone (>10 mg), methylprednisolone (>8 mg), dexamethasone (>1.5 mg)
- Anticonvulsants: phenytoin, carbamezepine, phenobarbital, oxcarbazepine
- HIV antivirals: efavirenz, nevirapine
- Antibiotics: rifampin (rifampicin), rifabutin, rifapentine
- Miscellaneous: St. John's Wort, modafinil, pioglitazone, troglitazone

Prohibited Medications

Subjects should not receive other anti-cancer therapy [cytotoxic, biologic, radiation (other than leuprolide or other GnRH agonists)] while on treatment in this study.

Medications that inhibit CYP3A4 may result in increased plasma pazopanib concentrations; therefore, co-administration of strong CYP3A4 inhibitors is **PROHIBITED** beginning 7 days prior to the first dose of study drug until discontinuation from the study. **Strong CYP3A4 inhibitors include (but are not limited to):**

- Antibiotics: clarithromycin, telithromycin, troleandomycin
- HIV: protease inhibitors (ritonavir, indinavir, saquinavir, nelfinavir, amprenavir, lopinavir)
- Antifungals: itraconzaole, ketoconazole, voriconazole, fluconazole
- Antidepressants: nefazodone
- Diet: grapefruit, seville oranges, starfruit, and their juices at or near time of drug ingestion

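### Estrogen suppression is required by study entry but not at the qualifying NSAI progression, so an endocrine change made in between can be credited to pazopanib

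*Combined protocol and SAP*

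**What the plan says.** Section 3.2 (Inclusion Criteria) deals with estrogen status and with prior progression in separate items that do not refer to each other.

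- **Item 4e:** "If premenopausal, must be on a GnRH agonist (leuprolide or goserelin) with serum estradiol levels within the institutional postmenopausal range". No start date, minimum duration or link to progression is given. Item 4c accepts bilateral oophorectomy, also undated.
- **Item 7a:** "Progression must be documented while taking a nonsteroidal aromatase inhibitor including anastrozole or letrozole". It says nothing about ovarian function or estrogen use at that time.
- **Items 7b and 7c:** these set minimum durations of hormonal therapy (6 months adjuvant, 3 months metastatic). Item 7c reads "If hormonal therapy was administered in the metastatic setting, subjects must have received therapy for at least 3 months prior to progression". Neither requires estrogen to have been suppressed during that period.
- **Item 10:** "Subjects must have discontinued hormone replacement therapy (HRT") "at least 28 days prior to receiving the first dose of randomized therapy". The anchor is first dose, not progression.

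Section 3.3, exclusion 2, bars "Premenopausal levels of estradiol, or ongoing menses (see definitions of menopause above"), which is a condition at enrollment. Section 11.1.4 exempts GnRH agonists from the ban on other anti-cancer therapy: "radiation (other than leuprolide or other GnRH agonists)] while on treatment in this study".

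Section 3.1 carries the patient's own NSAI forward from progression and names no other endocrine element. Section 12.0 sets the null below 5% for patients who receive nothing further after progressing on an aromatase inhibitor. It counts stable disease of at least 12 weeks as response and attributes 4 or more responders among 27 to the addition of pazopanib.

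**The concern.** The trial has no control arm, so its inference rests on pazopanib being the only change after NSAI progression. The criteria hold the NSAI constant but not the estrogen environment in which it was given. A woman who progressed on an NSAI without ovarian suppression, and then began a GnRH agonist or had an oophorectomy before Day 1, meets the criteria as written. So does a woman who stopped HRT in that interval.

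For such a patient the resistance that defines the population was not shown under estrogen suppression, and the null for no added treatment does not describe her. The change also bears on the pathway under test. Section 1.1 states: "These data indicate that estrogen acts directly on breast cancer cells to induce angiogenesis by creating a proangiogenic environment". Because 12 weeks of stable disease is enough to count, slowed growth from estrogen withdrawal would score in full. The bias in clinical benefit, and in progression-free survival, would be upward, and the bar is only four responders.

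**Working it through.** **Inputs from the plan (Sections 3.1 and 12.0).** Stage 1 has n1 = 14, continuing if at least 1 responds. Stage 2 adds n2 = 13, for 27 in total. Success is at least 4 responders. p0 = 0.05, p1 = 0.20, alpha 5%, power 80%.

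**Step 1: reproduce the stated design.** Write Bin(x; n, p) for the binomial probability.

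P(success | p) = Σ over x = 1..14 of Bin(x; 14, p) × P(Bin(13, p) ≥ 4 − x)

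At p = 0.05:

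- x = 1: 0.3593 × 0.0245 = 0.0088
- x = 2: 0.1229 × 0.1354 = 0.0166
- x = 3: 0.0259 × 0.4867 = 0.0126
- x ≥ 4: 0.0042

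The sum is 0.042, which meets the 5% limit. At p = 0.20 the same formula gives 0.807, which agrees with 80%. The plan's figures reproduce.

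**Step 2: margin in the null rate.** Solving P(success | p) = 0.05 gives p = 0.0528. One patient in 27 with a benefit rate of 20% makes the average null rate (26 × 0.05 + 1 × 0.20)/27 = 0.0556, already past that point.

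**Step 3: k affected patients.** Let k of the 27 have had an endocrine change after the qualifying progression, with 12-week benefit rate q from that change alone. Pazopanib is inert and the other 27 − k patients have rate 0.05. The k patients are placed at random across the two stages, so k1 fall in stage 1 with probability C(14, k1) × C(13, k − k1) / C(27, k). Within each stage the responder count is the sum of two binomials, one at q and one at 0.05. The Step 1 rule is then applied and averaged over k1.

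Both k and q are assumptions, because the documents give neither. The upper value of q takes a first-line median time to progression of about 9 months (Section 1.2 reports 8.9 and 9.4 months for anastrozole and letrozole) and an exponential curve: 12 weeks = 2.76 months, and 2^(−2.76/9) = 0.81.

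| k | q = 20% | q = 40% | q = 60% | q = 81% |
|---|---|---|---|---|
| 0 | 0.042 | 0.042 | 0.042 | 0.042 |
| 1 | 0.057 | 0.076 | 0.095 | 0.116 |
| 2 | 0.074 | 0.126 | 0.189 | 0.266 |
| 3 | 0.095 | 0.193 | 0.325 | 0.499 |

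**The case against.** **Timing.** A reader might infer that the endocrine change can begin together with pazopanib. The documents rule that out. Item 10 puts the HRT stop at least 28 days before first dose, and item 4e and exclusion 2 require estradiol to be out of the premenopausal range by entry. The change can fall only between the qualifying progression and Day 1. Its effect can still run through the 12-week window.

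**Plausibility.** Sections 1.1 and 1.2 present aromatase inhibitors as treatment for postmenopausal women, and Section 2.1 speaks of patients progressing on the same NSAI therapy. That suggests the authors meant an unchanged endocrine regimen. An NSAI given without ovarian suppression to a premenopausal woman would be unusual in that setting. Estrogen taken alongside an NSAI for breast cancer is remoter still, and item 10 reads as a generic washout. This limits the likely number of patients, and the HRT route deserves much less weight than items 4c and 4e. It does not close the gap, since no criterion excludes these patients.

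**Data capture.** Section 11.1.4 requires concomitant medications to be recorded with dates of administration, and Section 8.1 records medication from the 30 days before first dose. A GnRH agonist continued on study should therefore be traceable, although HRT stopped earlier may be missed. No planned analysis uses these records.

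**Stakes.** Section 12.0 claims only a possibility of reversing resistance, and Section 1.3 names a randomized phase II as the next step. That limits the harm of a false positive, but this trial's result is what would prompt that step.

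**Conclusion.** The gap is real. Items 4c and 4e, and less plausibly item 10, fix estrogen status by entry and not at the progression that defines resistance, and no analysis separates patients whose status changed in between.

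Its size is unknown. If no such patient enrolls, the false-positive rate stays at 0.042. One such patient takes it above 5% even at q = 20%. Across q from 20% to 81% the range is 0.057–0.116 for one, 0.074–0.266 for two and 0.095–0.499 for three. These figures assume an inert drug and a true 5% rate in everyone else.

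A reader might take the figure near 50% as the expected error. It is not: it needs three affected patients in 27 and full first-line sensitivity in women who have just progressed on endocrine therapy, and the documents support neither. Nor is this a fault in the sample-size arithmetic, which reproduces. The problem is attribution, and whether p0 fits everyone who can enroll.

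**What to change.** Reconcile items 4c, 4e and 10 with item 7a, so that the estrogen-suppression status required at entry was already in place when the qualifying NSAI progression was documented. No added minimum duration is needed for this purpose.

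If the sponsor prefers not to narrow eligibility, record the GnRH agonist start, oophorectomy and HRT stop dates relative to that progression. Then pre-specify a sensitivity analysis of the primary endpoint in which patients who changed after progression are counted as non-responders or excluded. Counting them as non-responders keeps the denominator of 27 and the cut-off of 4. Excluding them changes the denominator, so that version is better reported as an estimated rate than as a re-run of the decision rule.

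The cost is two or three sentences and perhaps a few premenopausal patients excluded, or else the date fields and one extra analysis. Sample size, cut-offs, alpha (0.042) and power (0.807) are unchanged.

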12.0 Statistical Considerations

The response rate with no additional treatment in women with disease progression while receiving aromatase inhibitors is expected to be <5%. We will consider an overall response rate of 20% to be clinically meaningful. For the purpose of this study, response will be defined as clinical benefit rate, including complete response, partial response, and stable disease for at least 12 weeks.

Therefore, we used the American Cancer Society's website (http://cryptnet.net/kepner/one_sample.html) for a 2 stage design with $p_0=0.05$, $p_1=0.20$ and power 80% at $\alpha=5\%$. This design specifies that if 0 of the first 14 eligible and evaluable subjects do not respond to the treatment at 12 weeks, then we are unlikely to reach a true overall response rate of 20%. The 15th patient will not be enrolled until we have confirmed that we have met criteria of at least 1 responses (response defined as clinical benefit) observed in the first 14 patients, to proceed to the second stage. An additional 13 patients will be enrolled in stage 2 for a total of 27 patients. If at least 4 of the total patients respond, we will conclude that the addition of pazopanib in this setting has the possibility of reversing resistance to hormone therapy with aromatase inhibitors. Using this design, we will have a less than 5% chance of incorrectly accepting the null hypothesis ($\alpha=0.05$), and an 80% chance of correctly rejecting the null hypothesis ($\beta=0.2$).

To determine whether the level of cytokines at baseline and during treatment could predict response to antiangiogenic therapy, we will divide patients into two groups; responder and non-responder group. The student t test will be used to analyze the differences of cytokine levels at baseline and at 4 weeks between these 2 groups.

CTC quantification data will be correlated with response and time to progression.

We will make preliminary observations regarding mutations or deletions in PIK3CA and PTEN in patients with measurable CTC, correlating changes with response and disease history, as well as presence or absence of these alterations in archival tumor tissue.

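### The 6- and 3-month minimum exposures in items 7b and 7c are not tied to the NSAI, so a patient given another hormonal agent first in the same setting can qualify after a few weeks on the NSAI

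*Combined protocol and SAP*

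**What the plan says.** Item 7 of Section 3.2 has three parts.

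- 7a names the drug class: "Progression must be documented while taking a nonsteroidal aromatase inhibitor including anastrozole or letrozole".
- 7b requires at least 6 months of adjuvant hormonal therapy before metastatic disease develops. It does not say which agent.
- 7c covers metastatic disease: "If hormonal therapy was administered in the metastatic setting, subjects must have received therapy for at least 3 months prior to progression". It does not say which agent either.

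No other section sets a minimum time on the NSAI.

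Sections 1.3, 2.1 and 3.1 describe the intended population more narrowly. These are patients progressing or relapsing on an NSAI who stay on that same NSAI while pazopanib is added.

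Section 12.0 gives the null rate for that population: "The response rate with no additional treatment in women with disease progression while receiving aromatase inhibitors is expected to be <5" percent. A response is CR, PR or stable disease for at least 12 weeks. The trial continues after 14 patients if at least one responds. It succeeds with at least 4 responders among 27, and the conclusion is then that adding pazopanib "has the possibility of reversing resistance to hormone therapy with aromatase inhibitors".

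**The concern.** The trial has one arm, so eligibility is the only thing that makes a 5% null credible. The null presumes that nearly every patient would progress within 12 weeks on the NSAI alone. A patient who took tamoxifen for a long time, switched to letrozole in the same setting and showed growth at a scan a few weeks later meets 7a to 7c as written. That growth may have occurred before letrozole could act. Some such patients could be stable at week 12 because of the NSAI, and each would count as a benefit of pazopanib.

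The wording can also fail in the other direction. A patient with 4 months of adjuvant tamoxifen and, later, two years of metastatic letrozole before progression fits the primary objective but fails 7b read literally.

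What is at stake is the type I error of the go decision and the meaning of a conclusion about reversing resistance.

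**Working it through.** **Inputs from Section 12.0.** The plan is a "2 stage design with $p_0=0.05$, $p_1=0.20$ and power 80" percent. Stage 1 has 14 patients, stage 2 has 13, and the total is 27. The trial continues with at least 1 benefit in 14 and succeeds with at least 4 in 27. The stated type I error is under 5% (the text describes it as a "less than 5% chance of incorrectly accepting the null hypothesis", which is a slip for rejecting it).

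**Step 1: reproduce the plan's figures.** With X1 ~ Bin(14, p) and X2 ~ Bin(13, p),

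P(success) = Σ P(X1 = x) · P(X2 ≥ 4 − x), summed over x ≥ 1.

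At p = 0.05:

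- x = 1: 0.3593 × 0.0245 = 0.0088
- x = 2: 0.1229 × 0.1354 = 0.0166
- x = 3: 0.0259 × 0.4867 = 0.0126
- x ≥ 4: 0.0042

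The sum is 0.0422. At p = 0.20 the same formula gives 0.8066. The stated alpha and power are therefore correct. The room below 5% is 0.050 − 0.042 = 0.008.

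**Step 2: who falls in the gap.** Take each setting in turn.

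| Hormonal history in the setting where progression occurred | Minimum NSAI exposure under 7b/7c |
|---|---|
| NSAI only, adjuvant | 6 months |
| NSAI only, metastatic | 3 months |
| Another agent first, then NSAI | None, provided total hormonal therapy reaches 6 or 3 months |

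Only the third row is open.

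**Step 3: effect on the false-positive rate.** Assume pazopanib is inert. Let k of the 27 patients have short NSAI exposure and a 12-week benefit rate q, and let the other 27 − k have rate 0.05. If k1 of the k fall in stage 1, then X1 is Bin(14 − k1, 0.05) plus Bin(k1, q), and X2 is formed in the same way from the rest. The result is averaged over k1 with weights C(14, k1)·C(13, k − k1)/C(27, k).

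Example, k = 1 and q = 0.20: 0.0574 if she is in stage 1 and 0.0559 if she is in stage 2, so 14/27 × 0.0574 + 13/27 × 0.0559 = 0.0567.

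| q (assumed) | k = 1 | k = 2 | k = 3 |
|---|---|---|---|
| 20% | 0.057 | 0.074 | 0.095 |
| 30% | 0.066 | 0.099 | 0.140 |
| 50% | 0.086 | 0.156 | 0.255 |
| 81% | 0.116 | 0.266 | 0.499 |

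Fixing the placement of three patients at two in stage 1 and one in stage 2 changes little: 0.096, 0.143 and 0.261 for q = 20%, 30% and 50%.

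The 81% row is an extreme. It comes from the first-line medians of 8.9 months (anastrozole) and 9.4 months (letrozole) in Section 1.2. Assuming exponential times and taking 12 weeks as 2.76 months, 2^(−2.76/8.9) = 0.807 and 2^(−2.76/9.4) = 0.816.

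**The case against.** **The gap is narrow.** Most patients whose only hormonal therapy in the setting was the NSAI are already held to 6 or 3 months of it. In 7c, the progression mentioned follows on from 7a, so a sensible investigator might read the 3 months as time on the NSAI. This stands as a limit on how many patients are affected. It does not cure the text, because 7b and 7c do not name the NSAI and no other section sets a minimum time on it.

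**A reader might infer that a patient who progressed on letrozole, was then controlled on chemotherapy and now restarts letrozole is eligible.** Item 7a has no recency condition. The listed washouts cover lapatinib, trastuzumab, HRT and radiotherapy (Section 3.2) and "Use of an investigational agent, including an investigational anti-cancer agent, within 14 days prior to the first dose of study drug" (Section 3.3), but not standard chemotherapy. The documents do not support that inference, however. Section 3.1 itself states eligibility in the present tense and requires the NSAI taken at progression to be continued, and Sections 1.3 and 2.1 agree. She is neither progressing on an NSAI nor continuing one. What remains is that the Section 3.2 list, which describes itself as the full set of conditions, does not carry this requirement.

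**A reader might also infer that three such patients make the go decision a coin toss.** That takes the 81% row at face value. The figure comes from unselected first-line patients, whereas every entrant here has documented growth on an NSAI. Section 1.3 also recognises intrinsic resistance, so early growth can be genuine resistance. The lower rows are more plausible, and no row is an estimate.

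**Conclusion.** The concern holds for exposure, and for recency only as a matter of carrying Section 3.1 into the checklist criteria. As written, 7b and 7c admit a patient with a few weeks of NSAI after another hormonal agent in the same setting. 7b can also exclude a patient who clearly fits the primary objective.

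The design has less than one percentage point of slack, so even one such patient with a 20% benefit rate takes the false-positive rate above 5% (0.057). Over one to three patients and rates of 20% to 50%, it runs from 0.057 to 0.255. These figures assume an inert drug, a true rate of exactly 5% in all other patients, and independent outcomes. The documents give neither the number of short-exposure patients nor their benefit rate, so whether they would decide the trial is unknown.

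The stated sample size, alpha and power are not wrong. This is a weakness in eligibility wording that should be repaired.

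**What to change.** 1. Reword 7b and 7c so that the existing 6- and 3-month minimums apply to the NSAI that will be continued on study, in the setting (adjuvant or metastatic) in which the qualifying progression occurred. The setting clause matters. Without it, 4 months of adjuvant letrozole followed by two years of metastatic letrozole would still fail 7b.
2. Carry the Section 3.1 condition into 7a: the patient is progressing on that same NSAI, this is her most recent progression, and no other systemic anticancer therapy was started after it. The anti-HER2 washouts in item 8 stay as they are.
3. Do not add a fixed number of weeks between progression and first dose. The documents offer no basis for one.
4. Update the eligibility checklist used at registration (Section 4.3) to match.

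The cost is a wording amendment and the loss of a few patients with short NSAI exposure, partly offset by patients whom 7b now excludes. The 27 evaluable and 30 enrolled patients, alpha of 0.042 and power of 0.807 are unchanged.
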